3.3 SELECTION OF TRIAL POPULATION

It is expected that 240 patients will be randomised from approximately 100 sites. Screening of patients for this trial is competitive, i.e. screening for the trial will stop at all sites at the same time once a sufficient number of patients has been screened. Investigators will be notified about screening completion and will then not be allowed to screen additional patients for this trial unless screening needs to be re-opened due to a higher rate of screen failures.

A log of all patients screened into the trial (i.e. who have signed informed consent) will be maintained in the Investigator Site File (ISF) irrespective of whether they have been treated with investigational drug or not.

If a patient is randomised in error (does not meet all inclusion criteria or meets one or more exclusion criteria), the sponsor should be contacted immediately.

3.3.1 Main diagnosis for trial entry

Diabetic kidney disease.

Please refer to [section 8.3.1](#) (Source Documents) for the documentation requirements pertaining to the in- and exclusion criteria.

3.3.2 Inclusion criteria

1. Signed and dated written informed consent in accordance with ICH-GCP and local legislation prior to admission to the trial.
2. Male or female patients aged ≥ 18 years at time of consent.
3. eGFR (Chronic Kidney Disease Epidemiology Collaboration [CKD-EPI] formula) ≥ 20 and < 90 mL/min/1.73 m² at Visit 1 by central laboratory analysis. eGFR must remain \geq

- 20 mL/min/1.73 m² after Visit 1 up to the start of Visit 3, measured by central or any local laboratory analysis.
4. UACR ≥ 200 and $< 3,500$ mg/g in spot urine (midstream urine sample) by central laboratory analysis at Visit 1.¹
 5. Treatment with the highest tolerated dose of either ACEi or ARB (but not both together), and stable dose for ≥ 4 weeks before Visit 1 with no planned change of the therapy during the trial.
 6. If the patient is taking any of the following medications they should be on a stable dose at least 4 weeks prior to visit 1 until start of treatment, with no planned change of the therapy during the trial: anti-hypertensives, NSAIDs, endothelin receptor antagonists, systemic steroids or SGLT2 inhibitors.
 7. Patients with stable type 1 or type 2 diabetes mellitus, diagnosed before informed consent. Treatment (including SGLT2 inhibitor and/or GLP1 receptor agonist) should have been unchanged or changes deemed minor (according to investigator's judgement) within 4 weeks before Visit 1 and until start of trial treatment.
 8. Glycated Haemoglobin (HbA1c) $< 10.0\%$ at Visit 1 measured by the central laboratory.
 9. Seated SBP ≥ 110 and ≤ 160 mmHg and DBP ≥ 65 and ≤ 110 mmHg at Visit 1 and optimized anti-hypertensive treatment according to local standard of care and investigator's judgement.²
 10. Body Mass Index (BMI) ≥ 18.5 and < 50 kg/m² at Visit 1.
 11. Male patients able to father a child must be willing to use condoms if their sexual partner is a Women of child-bearing potential³ (WOCBP). WOCBP must be ready and able to use highly effective methods of birth control per ICH M3 (R2). Such methods should be used throughout the trial. A list of contraceptive methods meeting these criteria is provided in the patient information and in [section 4.2.2.3](#) of the protocol.

3.3.3 Exclusion criteria

1. Treatment with Renin Angiotensin Aldosterone System (RAAS) interventions (apart from either ACEi or ARB), phosphodiesterase-5 inhibitors, non-specific phosphodiesterase inhibitors (such as dipyridamole and theophylline), NO donors including nitrates, sGC-stimulators/activators (other than trial treatment) or any other restricted medication (including OATP1B1/3 inhibitors, UGT inhibitors/inducers) as provided in the Investigator Site File (ISF) within 4 weeks prior to visit 1 and throughout screening and baseline run-in. Patients who must or wish to continue the intake of restricted medications (see [section 4.2.2.1](#)) or any drug considered likely to interfere with the safe conduct of the trial are also excluded.
2. Any clinically relevant laboratory value from screening until start of trial treatment, which in the investigator's judgement puts the patient at additional risk.
3. Biopsy or otherwise confirmed non-diabetic chronic kidney disease, or non-diabetic chronic kidney disease in the opinion of investigator, e.g., Autosomal Dominant Polycystic Kidney Disease (ADPKD), uncontrolled lupus nephritis. The presence of a hypertensive etiology does not need to be excluded unless it is evident this is the only cause for the CKD.
4. Any immunosuppression therapy or immunotherapy in the last 3 months prior to visit 1 and throughout screening and baseline run-in (except prednisolone ≤ 10 mg or equivalent).

5. Acute kidney injury (AKI) according to the Kidney Disease: Improving Global Outcomes (KDIGO) definition⁴ [[R17-2439](#)] in the 30 days prior to Visit 1 until the start of trial treatment.
6. Planned start of chronic renal replacement therapy during the trial or end stage renal disease before start of trial treatment.
7. Known history of moderate or severe symptomatic orthostatic dysregulation as judged by the investigator before start of trial treatment⁵.
8. The patient has an active infection with SARS-CoV-2 (or is known to have a positive test) from screening until randomisation.
9. Medical history of cancer or treatment for cancer in the last two years prior to Visit 1 (except appropriately treated basal cell carcinoma of the skin, in situ carcinoma of uterine cervix, and prostatic cancer of low grade [T1 or T2]).
10. Major surgery (investigator's judgement) planned during the trial.
11. History of clinically relevant allergy/ hypersensitivity that would interfere with trial participation including allergy to investigational product/ placebo or its excipients (see Investigator Brochure [[c02778238](#)])
12. Any other medical condition⁶ that in the investigator's opinion poses a safety risk for the patient or may interfere with the trial objectives.
13. Previous randomisation in this trial.
14. Currently enrolled in another investigational device or drug trial,
 - or less than 30 days or 5 half-lives (whichever is longer) prior to Visit 1 since ending another investigational device or drug trial(s) for an oral agent which is not specified in any other exclusion criteria,
 - or less than 12 months prior to Visit 1 since ending another investigational device or drug trial(s) for a biological agent which is not specified in exclusion criteria or restrictions table in [section 4.2.2](#),
 - or receiving other investigational treatment(s).
15. Chronic alcohol or drug abuse or any condition that, in the investigator's opinion, makes them an unreliable trial subject or unlikely to complete the trial.
16. Women who are pregnant, nursing or who plan to become pregnant while in the trial.
17. QTcF-interval > 450 ms in men or > 470 ms in women at any time from screening (Visit 1) until start of treatment.
18. A family history of long QT syndrome.
19. Concomitant use of therapies with a known risk of Torsade de Pointes at screening (Visit 1) and throughout screening and baseline run-in or planned initiation of such therapies during the trial (refer to [Section 4.2.2.1](#)).

¹In case of borderline out of range results UACR testing may be repeated once before the baseline sampling starts.

²A patient with a seated SBP between >160≤180 mmHG at Visit 1 may be re-screened according to the guidance in the [flow chart](#) and [section 6.2.2](#). Anyone with a SBP over 180mmHg should be excluded. This re-screening should only occur after appropriate adjustment to their medication and sufficient time to ensure their medication is stable in accordance with the protocol.

³A woman is considered of childbearing potential (WOCBP), i.e. fertile, following menarche and until becoming postmenopausal unless permanently sterile. Permanent sterilisation methods include hysterectomy, bilateral salpingectomy and bilateral oophorectomy. Tubal ligation is NOT a method of permanent sterilisation. A postmenopausal state is defined as no menses for 12 months without an alternative medical cause.

⁴Definition of AKI can be found in [section 3.3.4.1](#)

⁵Severity of symptomatic orthostatic dysregulation is based on the standard Adverse Event severity classification.

⁶Examples of medical conditions may include, but is not limited to:

- symptomatic heart failure (NYHA III/IV)
- known history of tachycardia and/or atrial fibrillation

- clinically relevant arrhythmias
- coronary heart disease not compensated by medical treatment (supine pulse rate > 70 beats per minute, existing angina pectoris).

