4.2.2 Restrictions

4.2.2.1 Restrictions regarding concomitant treatment

Mitigation of the potential risks can be achieved by close monitoring of patients and the prohibited co-administration of drugs with [REDACTED]. Special caution is warranted when administering BI 685509 in combination with drugs metabolized *via* CYP3A4, because the exposure of such drugs may potentially increase. In addition, BI 685509 must not be co-administered with OATP1B1/3 inhibitors and drugs known to inhibit or induce UGT enzymes, as this may impact BI 685509 exposures in a clinically relevant manner. List of relevant drugs can be found in the investigator site file.

In addition, intake of concomitant therapies with a known risk of Torsade de Pointes must not be co-administered with BI 685509 (also refer to [Table 1.4.2: 1](#)). These restrictions apply from screening (Visit 1), until Visit FUp3. In the event of temporary concomitant use of such a therapy, trial medication must be temporarily stopped and can then be re-started after a period of at least 5 half-lives after the concomitant therapy with the known risk of Torsade de Pointes has been stopped, as long as the interruption rules are followed. Refer to [Section 4.1.4.1](#) for rules for re-starting up-titration in case of interruption of trial medication.

Table 4.2.2.1: 1 Concomitant medication restrictions

Medication	Prior to trial (Visit 1)	During screening/ run-in	During Treatment Period	In the Follow-up Period
Either ACEi or ARB	Stable dose for ≥ 4 weeks before Visit 1 required combination of ACEi and ARB not allowed	Stable dose required; combination of ACEi and ARB not allowed	Stable dose required; combination of ACEi and ARB not allowed	Stable dose required; combination of ACEi and ARB not allowed

Table 4.2.2.1: 1 Concomitant medication restrictions cont.

Medication	Prior to trial (Visit 1)	During screening/ run-in	During Treatment Period	In the Follow-up Period
Other RAAS intervention	Not permitted within ≥ 4 weeks prior to visit 1	Not permitted	Not permitted	Not permitted
Anti-hypertensive treatment	During the 4 weeks prior to visit 1 permitted if the dose is stable throughout	Stable dose permitted	Stable dose permitted	Stable dose permitted

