* In case a sublingual nitrate is needed for suspected acute coronary syndrome, when the patient is on trial treatment, close monitoring of the blood pressure is required.

Table 4.2.2.1: 1 Concomitant medication restrictions cont.

Medication	Prior to trial (Visit 1)	During screening/ run-in	During Treatment Period	In the Follow-up Period
Other Investigational Medicinal Product or Investigational Device	Not permitted within 30 days or 5 half-lives (whichever is longer) prior to visit 1. Biologics are not permitted within 12 months prior to visit 1.	Not permitted	Not permitted	Not permitted
Treatment with clinically relevant OATP1B1/3 inhibitors and clinically relevant UGT inhibitors/ inducers as provided in the Investigator. Site File (ISF)	Not permitted within ≥ 4 weeks prior to visit 1	Not permitted	Not permitted	Permitted
Drugs with known risk of Torsade de Pointes	Not permitted at least 5 half-lives of such drug prior to visit 1	Not permitted	Not permitted	Not permitted
Herbal or natural products (Including Traditional Chinese Medicine)	Recommended to be stopped. Should not be initiated at or after screening	Initiation not permitted. If used at a stable dose prior to screening may be continued	Initiation not permitted. If used at a stable dose prior to screening may be continued	Initiation not permitted. If used at a stable dose prior to screening may be continued

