6.2.2 Screening and run-in period

Screening Period

No trial procedures should be done unless the patient has consented to taking part in the trial. Once informed consent is obtained, the patient is considered to be enrolled in the trial and have started screening. The patient should be recorded on the enrolment log and be registered in the IRT system as a screened patient before any other activities are performed. Patients who do not start the run-in period should be registered as a screen failure in the IRT system. Patients who do not fulfil all eligibility criteria for a reason that later resolves and allows eligibility criteria to be met, may be re-screened after discussion with the sponsor. Re-screening will only be allowed once.

The footnotes to the [flow chart](#) provide details about when screening procedures may be repeated and when re-screening is allowed.

Run-in Period

The run-in period for this trial lasts for two weeks prior to randomisation. During this period the patient will start to collect their UACR samples as described in the [flow chart](#) and in [section 5.1.1](#).

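### Exclusion 19 and the text of Section 4.2.2.1 restrict Torsade-risk drugs only from Visit 1, while the table in the same section also requires a washout of 5 half-lives before Visit 1

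*Protocol*

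**What the plan says.** Three places in the protocol set the pre-entry rule for drugs with a known risk of Torsade de Pointes.

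- Section 3.3.3, exclusion 19: "Concomitant use of therapies with a known risk of Torsade de Pointes at screening (Visit 1) and throughout screening and baseline run-in". Planned initiation during the trial also excludes, and the criterion ends with a reference to Section 4.2.2.1.
- Section 4.2.2.1, text: "These restrictions apply from screening (Visit 1), until Visit FUp3".
- Section 4.2.2.1, Table 4.2.2.1: 1, column for the time before Visit 1: "Not permitted at least 5 half-lives of such drug prior to visit 1".

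A fourth place may apply. Exclusion 1 covers other restricted medication "as provided in the Investigator Site File (ISF) within 4 weeks prior to visit 1 and throughout screening and baseline run-in", and also excludes "Patients who must or wish to continue the intake of restricted medications". It does not name Torsade-risk drugs, and the site-file list is not part of the documents.

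For use during treatment, the text of Section 4.2.2.1 has trial medication stopped temporarily; it "can then be re-started after a period of at least 5 half-lives after the concomitant therapy" has ended.

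**The concern.** The text of exclusion 19 and the text of Section 4.2.2.1 contain no washout before Visit 1; the table does. A patient who stopped such a drug shortly before Visit 1 satisfies the wording of exclusion 19 but not the table row.

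The numbered criteria decide eligibility. Section 3.3 defines randomisation in error by the inclusion and exclusion criteria, and Section 8.3.1 requires source evidence against them. Sites could therefore reach opposite decisions on the same patient, and a breach of the table row alone would not clearly count as an eligibility error.

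The rule concerns QT safety. Section 1.2 reports a QTcF effect in other trials of the compound, and the risk table in Section 1.4.2 cites Sections 3.3.3 and 4.2.2.1 as the mitigation. Two things are at stake: overlap of residual drug with the first dose, and the reference ECG. Section 3.3.4.1 measures the > 60 ms increase from the Visit 3 pre-dose value. If residual drug raises that value and then washes out, later increases on trial drug are understated.

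**Working it through.** **Wording.** The protocol gives no derived figure to reproduce, so the first step sets the windows side by side.

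| Place | Window before Visit 1 | From Visit 1 to first dose |
|---|---|---|
| Exclusion 19 | none stated; refers to 4.2.2.1 | excluded |
| 4.2.2.1 text | none; starts at Visit 1 | restricted |
| 4.2.2.1 table | at least 5 half-lives | not permitted |
| Exclusion 1, if the site-file list covers these drugs | 4 weeks | excluded |

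For other prohibited classes the numbered criterion repeats the table's window: 4 weeks (exclusion 1), 3 months for immunosuppression (exclusion 4), two years for cancer treatment (exclusion 9), and 30 days or 5 half-lives, or 12 months for biologics, for investigational products (exclusion 14). Exclusion 19 does not follow this pattern.

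**Timing.** Take a patient who stops the drug just before Visit 1. Inputs:

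- Shortest interval to first dose: about 14 days. Section 6.2.2 says "The run-in period for this trial lasts for two weeks prior to randomisation", and a flow chart footnote lets run-in start once screening procedures are done and results reviewed. Using the +/- 2 day window at Visit 2 gives 14 − 2 = 12 days. Both are lower limits, because time to obtain the screening results is not counted.
- Longest interval: 35 days, after which the patient is a screen failure (flow chart footnote).
- Half-lives: assumed, since the documents name no such drug and give no half-life. Elimination is taken as first order.

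Fraction left after 5 half-lives = 0.5^5 = 3.1%.

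Longest half-life for which 5 half-lives have passed by first dose = days / 5:

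- 12 / 5 = 2.4 days
- 14 / 5 = 2.8 days
- 35 / 5 = 7.0 days

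Fraction left at first dose = 0.5^(days / half-life):

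| Assumed half-life | 12 days | 14 days | 35 days |
|---|---|---|---|
| 1 day | 0.02% | 0.01% | < 0.01% |
| 2 days | 1.6% | 0.8% | < 0.01% |
| 4 days | 12.5% | 8.8% | 0.2% |
| 7 days | 30.5% | 25.0% | 3.1% |
| 10 days | 43.5% | 37.9% | 8.8% |

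**If exclusion 1 applies.** The drug-free time becomes 28 + 14 = 42 to 28 + 35 = 63 days, and the cut-off becomes 42 / 5 = 8.4 to 63 / 5 = 12.6 days (8.0 days at the window edge, from 40 / 5). Four weeks equals 5 half-lives at 28 / 5 = 5.6 days, so this lookback is longer than the table's window below that half-life and shorter above it.

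The eligibility conflict therefore does not depend on a long half-life, but the effect at first dose does.

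**The case against.** The strongest reply is that the washout is in the protocol and exclusion 19 points to the section that holds it. Section 4.2.1 also sends sites to the criteria and the table together for the full restrictions. Nothing expressly permits use up to the day before Visit 1, and a patient who meets the table row also meets the pre-entry part of exclusion 19. This stands in part: a careful site will find the table. It does not close the gap, because the section contradicts itself on the starting point, and the reference in exclusion 19 follows the clause on planned initiation, not any lookback.

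Existing safeguards also count. Exclusion 17 removes patients with QTcF above 450 ms (men) or 470 ms (women) at any time from Visit 1 until start of treatment. The > 500 ms stopping rule does not depend on baseline, and ECGs are taken at every treatment visit. These give partial protection; a raised reference below the exclusion 17 limits would still pass.

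A reader might infer three stronger things that the documents do not support:

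- That a patient can pass all the numbered criteria and start trial drug with any Torsade-risk drug still present. Exclusion 19 keeps the patient off such drugs throughout screening and run-in, so material residue needs a long half-life, and exclusion 1 may catch the patient first.
- That exclusion 1 sets a third, conflicting window. Whether it applies depends on the unseen site-file list. In the table, the row for OATP1B1/3 and UGT drugs cites that file and the Torsade row does not.
- That the entry rule is laxer than the restart rule. This is so only if the table is ignored. With the table, entry requires 5 half-lives before Visit 1 plus about two further weeks, which is stricter.

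**Conclusion.** The point holds as an inconsistency in the current text on a QT-safety entry rule. Exclusion 19 and the text of Section 4.2.2.1 start at Visit 1; the table starts at least 5 half-lives earlier. The cross-reference reduces the risk of divergent eligibility decisions but does not remove it.

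The consequence at first dose is limited. It needs a drug stopped shortly before Visit 1 with a half-life above about 2.4 to 2.8 days at the shortest interval or 7 days at the longest; if exclusion 1's four weeks apply, the cut-offs rise to 8.4 and 12.6 days (8.0 at the window edge). All of this rests on assumed half-lives and first-order elimination. The effect on the Visit 3 QT/QTcF reference is a plausible direction of bias; the documents do not allow its size to be calculated. Which window is right is not judged here.

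**What to change.** Reconcile exclusion 19, the text of Section 4.2.2.1 and the Torsade row of Table 4.2.2.1: 1 so that one pre-entry window holds, and state that window in the numbered exclusion criterion. Clarify at the same time whether exclusion 1, through the site-file list, applies to these drugs. The choice of window is for the sponsor.

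The cost is a short wording change in an amendment and possibly a few delayed screenings. The protocol already allows one re-screening.

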3.3.4 Withdrawal of patients from treatment or assessments

Patients may discontinue trial treatment or withdraw consent to trial participation as a whole (“withdrawal of consent”) with very different implications; please see [sections 3.3.4.1](#) and [3.3.4.2](#) below.

Every effort should be made to keep the patients in the trial: if possible on treatment, or at least to collect important trial data (UACR and eGFR sampling) according to the [flow chart](#). Measures to control the withdrawal rate include careful patient selection, appropriate explanation of the trial requirements and procedures prior to trial enrolment, as well as the explanation of the consequences of withdrawal.

The decision to discontinue trial treatment or withdraw consent to trial participation and the reason must be documented in the patient files and CRF. If applicable, consider the requirements for Adverse Event collection reporting (please see [sections 5.2.6.2.1](#) and [5.2.6.2.2](#)).

3.3.4.1 Discontinuation of trial treatment

An individual patient will discontinue trial treatment if:

- The patient wants to discontinue trial treatment, without the need to justify the decision.
- The patient has repeatedly shown to be non-compliant with important trial procedures and, in the opinion of both, the investigator and sponsor representative, is not willing or able to adhere to the trial requirements in the future.
- The patient needs to take concomitant medication that interferes with the safety of the investigational medicinal product, refer to [sections 4.2.1](#) and [4.2.2](#). If there is no safety concern then the Sponsor will review on a case-by-case basis as to whether it is appropriate for the patients to continue. This decision will be based on factors such as duration of treatment, dose etc. If the patient needs to modify a dose, where a stable dose is permitted only, this will not automatically require a discontinuation. In this case the sponsor should be consulted.
- The patient develops Acute Kidney Injury as per clinical judgment by the Investigator. The Kidney Disease: Improving Global Outcomes (KDIGO) definition [[R17-2439](#)] should be used for guidance:
 - Increase in serum creatinine by ≥ 0.3 mg/dL (≥ 26.5 $\mu\text{mol/L}$) within 48 hours; or
 - Increase in serum creatinine to ≥ 1.5 times, which is known or presumed to have occurred within the prior 7 days; or
 - Urine volume < 0.5 mL/kg/h for 6 hours.
- The patient progresses to end stage renal disease and needs to obtain renal replacement therapy.
- Patients with a QT or QTcF interval > 500 ms, or an increase of QT or QTcF of > 60 ms from the pre-dose value at Visit 3 (baseline). Such cases must be reported as AEs.
- The patient experiences a severe infection, e.g. with SARS-CoV-2 that precludes their safe participation in the trial, as determined by the investigator.

- The patient can no longer receive trial treatment for any other medical reasons such as surgery, serious or severe Drug Induced Liver Injury (DILI) attributable to the trial drug (see [section 5.2.6.1.4](#)), other adverse events, or other diseases.
- The patient has discontinued trial treatment for at least 10 consecutive days* or has not taken medication at a total of 14 days* during the trial. In case of a temporary reason, trial treatment should be restarted if medically justified, please see [section 4.1.4](#) for dose adjustments. * *a missed day is classed as all 3 doses being missed*
- A female patient becomes pregnant. The patient will be followed up until birth or otherwise termination of the pregnancy. The data of the patient will be collected and reported in the clinical trial report until last patient last visit and any events thereafter will be reported in the BI Pharmacovigilance database. See [section 5.2.6.2.3](#).

If new efficacy/safety information becomes available, Boehringer Ingelheim will review the benefit-risk-assessment and, if needed, pause or discontinue the trial treatment for all patients or take any other appropriate action to guarantee the safety of the trial patients.

Please see [section 6.2.4](#) for details of the procedures to be performed if trial treatment is discontinued.

The sponsor may decide to replace patients if patients terminate early due to a pandemic outbreak.

